7.3 Handling of Dropouts or Missing Data

Missing 12 week efficacy data will be imputed and subsequently analyzed. The primary method of handling missing efficacy data will be the method of MCMC multiple imputation which does not rely on the assumption of data missing at random. Additionally, the pattern of missing observations in each treatment group will not influence the missing value estimation in the other because the imputation will be conducted independently for each treatment group.

The multiple imputation process for imputing missing lesion count and IGA data and subsequent analysis will involve 4 distinct phases with these principal tasks:

- 1. Calculate the number of missing 12-week values for each treatment group to be estimated by MCMC. Let nmiss be the maximum number of missing between the two treatment groups.
- 2. Create a data set of subjects, one for each treatment group, with observed values and those needing estimation by MCMC. The missing values in each data set will be filled in using the MCMC method '5 x nmiss' times to generate '5 x nmiss' data sets. The resulting data sets for each treatment arm will be combined into one complete data set for each imputation.
- 3. For each complete data set, compute the necessary derived variables. Each complete data set will be analyzed with the appropriate analysis model. See Sections 7.3.1.1 and 7.3.1.2 for details.
- 4. The results from these analyses will be combined into a single inference using SAS PROC MIANALYZE.

Sensitivity analyses will be performed on the primary efficacy endpoints to investigate the impact of the method of imputation. The first set of sensitivity analyses will use repeated measures. See Sections 7.3.2.1 and 7.3.2.2 for details.

The second set of sensitivity analyses will use model-based multiple imputation. The model-based multiple imputation process requires the data to have a monotone missing pattern. However, the imputation model will include treatment group and analysis center, and for lesion counts will include a covariate of baseline lesion count. Since treatment group, analysis center and baseline lesion count will be non-missing, the data will have a monotone missing pattern. The model-based multiple imputation process will involve 4 principal tasks:

- 1. Calculate the number of missing 12-week values to be imputed (nmiss).
- 2. Missing values will be filled in '5 x nmiss' times to generate '5 x nmiss' complete data sets. The imputation model used will be the analysis model.
- 3. For each complete data set, compute the necessary derived variables. Each complete data set will be analyzed with the appropriate analysis model. See Sections 7.3.2.1 and 7.3.2.2 for details.
- 4. Results from these analyses will be combined into a single inference using SAS PROC MIANALYZE.

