11.7 Missing Efficacy Data Imputations

Lesion Count Variable Missing Data Imputation

Missing 12 week data will be estimated by multiple imputation and subsequently analyzed. Missing lesion count data will be derived for the analysis using the method of Markov Chain Monte Carlo (MCMC) multiple imputation which does not rely on the assumption of data missing at random. Additionally, the pattern of missing observations in each treatment group

cannot influence the missing value estimation in the other because the imputation is being conducted independently for each treatment group.

Multiple imputation and subsequent analysis will involve 4 distinct phases with these principal tasks:

- 1. Calculated the number of missing values to be estimated by MCMC (nmiss) for 12-week value.
- 2. Create a data set of subjects, one for each treatment group, with observed values and those needing estimation by MCMC. The missing lesion count values in each data set will be filled in using the MCMC method '5 x nmiss' times to generate '5 x nmiss' data sets. The resulting data sets for each treatment arm will be combined into one complete data set for each imputation.

```
Syntax:
```

```
proc mi data=datain out=dataout seed=&seed. Nimpute=5xnmiss <options>; where trtpn=(1, or 2); mcmc chain=multiple; var baseline week4 week8 week12; run;
```

- 3. For each complete data set, the absolute change in lesion counts for baseline minus the 12-week value will be computed. Each complete data set will be analyzed as specified for the particular analysis.
- 4. The results from these analyses will be combined into a single inference using SAS PROC MIANALYZE.

A total of 4 random seeds will be needed to impute inflammatory lesion counts and fcnon-inflammatory lesion counts for the two treatment groups. Those 4 random seeds have been prespecified by using a random number generator:

- Inflammatory Lesion Counts; Olumacostat Glasaretil Gel: Seed= 195361148
- Inflammatory Lesion Counts; Olumacostat Glasaretil Gel Vehicle: Seed= 2099102059
- Non-Inflammatory Lesion Counts; Olumacostat Glasaretil Gel: Seed= 325230329
- Non-Inflammatory Lesion Counts; Olumacostat Glasaretil Gel: Seed= 936128187

IGA Missing Data Imputation

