A similar procedure will be used for the analyses based on proportion of IGA successes wherein the ANCOVA analysis is replaced with a logistic regression analysis. Specifically, missing 12-week IGA values from which the dichotomized IGA is derived will be estimated by (MCMC) which does not rely on the assumption of data missing at random. Additionally, the pattern of missing observations in each treatment group cannot influence the missing value estimation in the other because the imputation is being conducted independently for each treatment group.

The missing 12-week IGA values will be derived for the analysis using the method of Markov Chain Monte Carlo (MCMC) multiple imputation. Multiple imputation and subsequent analysis will involve 4 principal tasks:

- 1. Calculate the number of missing values to be estimated by MCMC (nmiss) for 12-week value.
- 2. Create a data set, one for each treatment group, of subjects with observed values and those needing estimation by MCMC. The missing IGA values in each data set will be filled in using the MCMC method '5 x nmiss' times to generate '5 x nmiss' data sets. The resulting data sets for each treatment arm will be combined into one complete data set by imputation.

```
Syntax:
```

```
proc mi data=datain out=dataout seed=&seed. Nimpute=5xnmiss <options>; where trtpn=(TRT); /* Note TRT = [1, 2]; depending on treatment group */; mcmc chain=multiple; var baseline week4 week8 week12; run;
```

- 3. For each complete data set, the dichotomous success rate (clear or almost clear with a 2-point change from baseline) will be computed. The 12-week estimated global values will be rounded to the nearest integer value prior to evaluating the success rate. Each complete data set will be analyzed with a logistic regression with factors of treatment group and analysis center.
- 4. The results from these analyses will be combined into a single inference using SAS PROC MIANALYZE.

A total of 2 random seeds will be needed to impute IGA for the two treatment groups. Those 2 random seeds have been pre-specified by using a random number generator:

- IGA; Olumacostat Glasaretil Gel: Seed= 322979853
- IGA: Olumacostat Glasaretil Gel Vehicle: Seed= 1313477781

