5. CHANGES IN THE CONDUCT OF THE STUDY OR PLANNED ANALYSES

There are no changes in the conduct of the study, but there are minor changes to the planned analyses.

The pooling analysis described in the protocol is updated in the statistical analysis plan (SAP) to reflect the intended analysis. The protocol discusses pooling sites with five or fewer subjects enrolled in each treatment arm. Taking into consideration the randomization ratio, the SAP requires ten subjects in the active treatment arm and five subjects in the vehicle group. The SAP also clarifies the pooling of sites will be performed for each country separately.

As part of the pooling analysis, the treatment effect within investigational site must be investigated. The protocol states the site main effect will be examined by using a one-way analysis of variance (for lesion count variables) or a logistic regression analysis (for dichotomized IGA) with a factor of site. The SAP instead explains site will be incorporated into the primary analysis models. Change from Baseline in lesion counts will be analyzed with an analysis of covariance (ANCOVA) (unranked or ranked) with factors of treatment group, investigational site and treatment group by investigational site interaction, and the respective baseline lesion count variable as a covariate. The dichotomized primary endpoint will be analyzed with a logistic regression with factors of treatment group, investigational site and the interaction term of treatment group by investigational site.

The protocol describes repeated measures sensitivity analyses for the primary efficacy endpoints. Treatment group, analysis center and visit are listed as factors for the repeated measures analyses. In addition to these factors, the SAP includes a factor of treatment group by visit interaction.

A subgroup summary of oral contraceptive used was added. Specifically, subjects will be categorized as Oral Contraceptives Approved for Acne Treatment Usage and No Oral Contraceptives Approved for Acne Treatment Usage.

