7.3.1 MCMC Multiple Imputation

7.3.1.1 Lesion Count Variable Missing Data Imputation

A total of 4 random seeds will be needed to use PROC MCMC to impute inflammatory lesion counts and non-inflammatory lesion counts for the two treatment groups. Those 4 random seeds have been pre-specified by using a random number generator:

- Inflammatory Lesion Counts; Olumacostat Glasaretil Gel, 5.0%: Seed= 195361148;
- Inflammatory Lesion Counts; Olumacostat Glasaretil Gel, Vehicle: Seed= 2099102059;
- Non-Inflammatory Lesion Counts; Olumacostat Glasaretil Gel, 5.0%: Seed= 325230329;
- Non-Inflammatory Lesion Counts; Olumacostat Glasaretil, Vehicle: Seed= 936128187.

After imputing with PROC MCMC, the absolute change in lesion counts for Baseline minus the 12-week value will be computed. Each complete data set will be analyzed with an ANCOVA with factors of treatment group and analysis center and the respective baseline lesion count as a covariate. A factor of treatment group by analysis center will be added if necessary, and appropriate modifications will be made should the analysis be based on a non-parametric method. The results from these analyses will be combined using SAS PROC MIANALYZE.

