7.3.1.2 IGA Missing Data Imputation

A total of 2 random seeds will be needed to impute IGA for the two treatment groups. Those 2 random seeds have been pre-specified by using a random number generator:

- IGA; Olumacostat Glasaretil Gel, 5.0%: Seed= 322979853;
- IGA; Olumacostat Glasaretil Gel, Vehicle: Seed= 1313477781.

After imputing with PROC MCMC, the dichotomous success rate (clear or almost clear with at least a 2-point change from Baseline) will be computed. The 12-week estimated IGA values will be rounded to the nearest integer value prior to evaluating the success rate. Each complete data

set will be analyzed with a logistic regression with factors of treatment group and analysis center. The results from these analyses will be combined using SAS PROC MIANALYZE.

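### The primary imputation is said not to need missing at random, but as specified it does, and no planned analysis examines departures from that assumption

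*SAP*

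**What the plan says.** SAP 7.3 names MCMC multiple imputation as the primary method and describes it as "the method of MCMC multiple imputation which does not rely on the assumption of data missing at random". Protocol 11.7 says the same for lesion counts ("multiple imputation which does not rely on the assumption of data missing at random") and for IGA ("will be estimated by (MCMC) which does not rely on the assumption of data missing at random"). Both documents add that each arm is imputed separately, so one arm's missing pattern cannot affect the other.

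The only imputation code is in Protocol 11.7. It is a PROC MI call for one arm at a time, containing "mcmc chain=multiple; var baseline week4 week8 week12; run". The SAP names a different SAS procedure: "4 random seeds will be needed to use PROC MCMC to impute inflammatory lesion counts" in 7.3.1.1 and "After imputing with PROC MCMC, the dichotomous success rate" in 7.3.1.2. It gives no variable list. SAP 5 says that "there are minor changes to the planned analyses", but none of those listed concerns imputation.

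The sensitivity analyses are intended "to investigate the impact of the method of imputation". They are:

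- repeated-measures ANCOVA for lesion counts and GEE for IGA, both on observed data;
- model-based imputation from treatment and analysis center, plus baseline count for lesions.

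Efficacy analyses are also repeated in the per-protocol set.

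**The concern.** MCMC is a way of drawing from a model. It does not relax the assumption about why data are missing. In the protocol's code, a multivariate normal model is fitted to the observed values and missing values are drawn from it. The draws are right only if, within arm, missingness at Week 12 depends on the baseline, Week 4 and Week 8 values and not on the unseen Week 12 value. Imputing by arm stops the arms informing each other but leaves that assumption in place.

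A reader would therefore credit three co-primary analyses in a confirmatory trial with a protection they lack. The plan itself foresees exits linked to outcome. SAP 7.8.4 mentions subjects who stop because treatment is documented as not working. Protocol 10.2 removes subjects who need prohibited treatment.

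Early Termination assessments and retained post-treatment data (SAP 7.9, 7.9.2) shrink the unseen part but do not remove it. An Early Termination assessment maps to Week 12 only on Days 71 to 98, so an earlier exit without follow-up leaves Week 12 to be imputed.

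**Working it through.** **1. What each planned analysis assumes**

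| Analysis | Source | Assumption about missing Week 12 |
|---|---|---|
| Primary: by-arm imputation on baseline, Weeks 4, 8, 12 | Protocol 11.7 | MAR given those values, within arm |
| Repeated-measures ANCOVA, counts | SAP 7.3.2.1 | MAR if likelihood-based (estimation method not stated) |
| GEE, IGA, no weighting stated | SAP 7.3.2.2 | Generally stronger: missing completely at random or dependent on covariates only |
| Model-based imputation | SAP 7.3, 7.3.2 | Stronger: Weeks 4 and 8 are left out |
| Per-protocol repeat | SAP 7.8.4 | Changes the population, not the assumption |

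Neither document contains a shift, reference-based, pattern-specific or missing-as-failure analysis.

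**2. The plan's own figures (SAP 4.2)**

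- Non-inflammatory: difference 14.73 - 9.70 = 5.03, SD 16.72, 450 vs 225. SE = 16.72 × √(1/450 + 1/225) = 1.365; 5.03/1.365 - 1.96 = 1.72; power 95.8%. The stated 95% reproduces.
- Inflammatory: difference 15.21 - 9.7 = 5.51, SD 11.00, 300 vs 150: power 99.9%, consistent with at least 95%.
- IGA: 20.5% vs 9.6%, continuity-corrected: 222 vehicle subjects, an exact match.
- Margin for missing data, non-inflammatory: 1 - 675/700 = 3.6%. No dropout rate is stated.

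**3. Does the specified method depend on MAR?**

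Large-sample simulation, 300,000 per arm, true non-inflammatory difference 5.03, SD 16.72. Assumed:

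- correlation 0.3 between baseline and change, and 0.5 to 0.8 between adjacent visits;
- log-odds of dropout rising by 1 or 2 per SD of poorer response;
- the same missing rate in each arm, with only Week 12 missing.

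The 15.5% rate is illustrative. Positive differences favour active.

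| Dropout depends on | 3.6% missing | 5% | 15.5% |
|---|---|---|---|
| Observed Week 8 | 5.0-5.1 | 5.0-5.1 | 5.0-5.1 |
| Unseen Week 12, both arms equally | 5.0-5.1 | 5.0-5.1 | 5.0-5.1 |
| Unseen Week 12, active only | 5.2-5.8 | 5.3-6.0 | 5.9-7.7 |
| Unseen Week 12, vehicle only | 4.3-4.8 | 4.1-4.8 | 2.3-4.2 |

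A second simulation used 467/233, 20 imputations, 600 trials and about 12% missing, with an assumed SD of 15 and correlation of 0.6. It gave 4.97 (Monte Carlo SE 0.05) under dropout on Week 8. It gave 5.76 (SE 0.05) when active-arm dropout depended on unseen Week 12, which is 5.76 - 5.03 = 0.73 too high, about 15%.

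**4. Would the planned sensitivity analyses reveal it?**

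Repeated measures with an unstructured covariance (assumed; the SAP states none) stays within 0.11 of the primary in every scenario. Model-based imputation moves, but not informatively. At 15.5% missing, correlation 0.6 and the stronger dropout, it differs from the primary by 1.8 when the primary is right, and by only 0.8-0.9 when the primary is about 2.4 too high.

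**5. How far would missing values have to depart?**

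Tipping point = (difference - 1.96 × SE) / missing rate, shifting only missing active subjects. With 467/233, √(1/467 + 1/233) = 0.0802, so SE = 1.341 (non-inflammatory) and 0.882 (inflammatory). The lower figure divides SE by √(1 - missing rate). Example at 5%: (5.03 - 2.63)/0.05 = 48; with the larger SE, (5.03 - 2.70)/0.05 = 47.

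| Missing | Non-inflammatory | Inflammatory |
|---|---|---|
| 3.6% | 66-67 | 105-106 |
| 5% | 47-48 | about 75 |
| 10% | 23-24 | 37-38 |
| 15.5% | 14-16 | 23-24 |

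Finite-sample check (300 trials, 15.5% missing, shift 14.7): mean estimate 2.64, 48% of trials significant. That is what a tipping point should give, since 1.96 × 1.341 = 2.63.

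For IGA, the bounds on the 10.9-point difference are 20.5 × (1 - m) - 9.6 (all missing active subjects fail) and 20.5 - 9.6 × (1 - m) (all missing vehicle subjects fail). They are 9.9 to 11.4 points at 5% and 7.7 to 12.4 at 15.5%.

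**The case against.** The sentence cannot be defended, but its weight can be disputed.

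- **Exposure is limited.** If every missing active subject is counted as an IGA failure and vehicle stays at 9.6%, the continuity-corrected p-value at 467/233 is about 0.001 at 5% missing, about 0.01 at 15.5% and still just under 0.05 at 25%. The inflammatory tipping point at 15.5% exceeds the whole planned active change of 15.21. That leaves the non-inflammatory count, at a rate about four times the plan's margin. This stands.
- **Large biases need strong assumptions.** They require outcome-driven dropout confined to one arm; equal dropout gives none. This stands: neither direction nor size can be known from the documents.
- **The repeated-measures results rest on an assumed covariance, and ranked analyses were not simulated.** This stands. Lesion-scale biases may not carry over if the skewness test triggers ranking.
- **PROC MCMC is probably a naming slip.** The seed values match the protocol's. It is likely a slip, but the SAP should still name the procedure and variables.
- **The stated aim was only to vary the imputation method.** The planned analyses do that, but only under MAR or stricter assumptions. That does not support a claim to be free of MAR.
- **Editing the protocol means an amendment reviewed by the ethics board (Protocol 12.1).** A correction recorded in SAP 5 can serve instead.

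None of this makes the sentence true or supplies the missing analysis.

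**Conclusion.** The concern holds. The plan states a property that its primary analysis does not have, and nothing planned examines departures from MAR. The estimates need not be biased: the primary is right if dropout follows observed visits, and the simulated difference is also unbiased if outcome-driven dropout is equal in the two arms.

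At the planned effects, the matter is minor near 3.6% to 5% missing. It grows with the missing rate and mainly concerns non-inflammatory counts. Near 15.5%, a shift about as large as the planned active change of 14.73 would remove significance. Missing rates, visit correlations and dropout mechanisms are all assumptions. This should be fixed before unblinding, but it does not call for a different primary analysis.

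**What to change.** 1. In SAP 7.3, state that the primary imputation assumes data are missing at random given baseline, Week 4 and Week 8 values within treatment group. Correct both statements in Protocol 11.7, by amendment or through an entry in SAP 5.
2. Reconcile the procedure named in SAP 7.3.1.1 and 7.3.1.2 with the protocol's PROC MI, and put the variable list in the SAP.
3. Before unblinding, add one MNAR analysis for both lesion counts and IGA. Apply it only to missing Week 12 values and keep all observed post-treatment data. Either option would do:
   - **Delta-adjusted tipping point.** Worsen imputed Week 12 counts over a pre-stated range, separately in each arm. An example is 0 to 15 lesions, about loss of the planned active mean change. If nothing tips within that range, that is itself the finding. Apply the shift before any ranking and use the model chosen for the primary. For IGA, shift before rounding or vary the success rate among missing subjects by arm.
   - **Vehicle-based imputation** for active subjects with missing Week 12, run separately.

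The cost is wording and modest programming across three endpoints, with no new data, visits or subjects. The downside is one more supplementary result, which may look less favourable.

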7.3.1 MCMC Multiple Imputation

7.3.1.1 Lesion Count Variable Missing Data Imputation

A total of 4 random seeds will be needed to use PROC MCMC to impute inflammatory lesion counts and non-inflammatory lesion counts for the two treatment groups. Those 4 random seeds have been pre-specified by using a random number generator:

- Inflammatory Lesion Counts; Olumacostat Glasaretil Gel, 5.0%: Seed= 195361148;
- Inflammatory Lesion Counts; Olumacostat Glasaretil Gel, Vehicle: Seed= 2099102059;
- Non-Inflammatory Lesion Counts; Olumacostat Glasaretil Gel, 5.0%: Seed= 325230329;
- Non-Inflammatory Lesion Counts; Olumacostat Glasaretil, Vehicle: Seed= 936128187.

After imputing with PROC MCMC, the absolute change in lesion counts for Baseline minus the 12-week value will be computed. Each complete data set will be analyzed with an ANCOVA with factors of treatment group and analysis center and the respective baseline lesion count as a covariate. A factor of treatment group by analysis center will be added if necessary, and appropriate modifications will be made should the analysis be based on a non-parametric method. The results from these analyses will be combined using SAS PROC MIANALYZE.

7.3.1.2 IGA Missing Data Imputation

A total of 2 random seeds will be needed to impute IGA for the two treatment groups. Those 2 random seeds have been pre-specified by using a random number generator:

- IGA; Olumacostat Glasaretil Gel, 5.0%: Seed= 322979853;
- IGA; Olumacostat Glasaretil Gel, Vehicle: Seed= 1313477781.

After imputing with PROC MCMC, the dichotomous success rate (clear or almost clear with at least a 2-point change from Baseline) will be computed. The 12-week estimated IGA values will be rounded to the nearest integer value prior to evaluating the success rate. Each complete data

set will be analyzed with a logistic regression with factors of treatment group and analysis center. The results from these analyses will be combined using SAS PROC MIANALYZE.

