4.2 Determination of Sample Size

The sample size for this study was based on estimates from the DRM01B-ACN02 study observed Week 12 results. Estimates were combined for all three active treatment groups as well as for the two vehicle groups. All power calculations were performed with nQuery Advisor Version 7.0 for a two-sided test at alpha = 0.05.

For inflammatory lesion change a sample size of 300 Olumacostat Glasaretil Gel and 150 Olumacostat Glasaretil Gel, Vehicle subjects has at least 95% power to detect a statistically significant difference with a significance level of 0.05 using the estimated absolute change from Baseline in treatment means of -15.21 and -9.7 for Olumacostat Glasaretil Gel versus its vehicle, respectively, with a standard deviation (SD) of 11.00.

For non-inflammatory lesion change a sample size of 450 Olumacostat Glasaretil Gel and 225 Olumacostat Glasaretil Gel, Vehicle subjects has 95% power to detect a statistically significant difference with a significance level of 0.05 using the estimated absolute change from Baseline in treatment means of -14.73 and -9.70 for Olumacostat Glasaretil Gel versus its vehicle, respectively, with a SD of 16.72.

The success rate for dichotomized IGA is estimated to be 20.5% in the Olumacostat Glasaretil Gel subjects and 9.6% in vehicle subjects. A sample size of 444 Olumacostat Glasaretil Gel and 222 Olumacostat Glasaretil Gel, Vehicle will have 95% power to detect a statistically significant difference in proportions of successes. These calculations were performed with nQuery Advisor Version 7.0 for a two-sided continuity corrected chi-square test at alpha = 0.05.

To allow for a slight loss in power due to dropouts and withdrawals as well as to accommodate sufficient power in all three co-primary variables, a sample of 700 subjects randomized to 2 to 1 for Olumacostat Glasaretil Gel (n=467) and vehicle (n=233), respectively, will be enrolled in the trial.

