7. STATISTICAL METHODS AND ANALYSIS

7.1 General Methodology

All analyses will be performed using SAS® Version 9.3 or later. No interim analyses are planned. Except where noted, all statistical tests will be two-sided and will be performed at the 0.05 level of significance.

Descriptive statistics will be used to provide an overview of the efficacy and safety results. For categorical parameters, the number and percentage of subjects in each category will be presented. For continuous parameters, descriptive statistics will include n (number of observations), mean, SD, median, minimum and maximum. Appropriate inferential statistics will be used for the primary, secondary and exploratory efficacy variables.

The primary method of handling missing efficacy data will be the method of Markov Chain Monte Carlo (MCMC) multiple imputation.

The primary method of dichotomizing the IGA score will be to consider a subject a "success" if the IGA at a post-baseline visit is 0 or 1 and 2 or more grades lower than at Baseline; otherwise the subject will be considered a treatment "failure".

Reported AEs, medical history terms, prior and concomitant procedures and therapies and washout procedures will be classified on the basis of Medical Dictionary for Regulatory Activities (MedDRA) terminology, Version 19.1. Prior and concomitant medications and washout medications will be classified on the basis of World Health Organization Drug Dictionary (WHO-DDE) terminology, Format B2, Version March 1, 2016.

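### The primary IGA imputation draws the five-grade score from a normal model and rounds it, which misstates the success rate of imputed subjects; the effect on the treatment difference is small, and ordinal imputation is a cheap improvement

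*SAP*

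**What the plan says.** SAP 7.3 sets the status of the method: "The primary method of handling missing efficacy data will be the method of MCMC multiple imputation". It is run separately in each arm. IGA success is one of three co-primaries; SAP 4.2 sizes the trial "to accommodate sufficient power in all three co-primary variables".

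The only imputation code is in Protocol 11.7, a PROC MI call containing "mcmc chain=multiple; var baseline week4 week8 week12; run". It is applied to the IGA grade, not to success or failure. Success is derived afterwards, and the Protocol says: "The 12-week estimated global values will be rounded to the nearest integer value prior to evaluating the success rate". SAP 7.3.1.2 repeats the rule ("The 12-week estimated IGA values will be rounded to the nearest integer value prior to evaluating the success rate"), names the procedure as PROC MCMC and states no other model.

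SAP 7.1 defines success as "the IGA at a post-baseline visit is 0 or 1 and 2 or more grades lower than at Baseline". SAP 7.7 confirms that eligibility limits baseline to 3 or 4.

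SAP 7.3.2.2 adds two IGA sensitivity analyses that do not round: a GEE on observed dichotomised data, and logistic multiple imputation of the binary Week 12 outcome from treatment and analysis center.

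**The concern.** The MCMC statement in PROC MI fits a joint normal distribution, whereas IGA has five ordered grades and few subjects are expected at the success end. For a baseline of 3 or 4, primary success means Week 12 grade 0 or 1. After rounding, that is a draw below 1.5. A normal curve with the right mean and SD need not put the right area below 1.5, particularly if many subjects stay at grade 3.

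The reported success rates of a co-primary endpoint, and possibly the difference between arms, are at stake. The error is systematic, so generating five times as many data sets as there are missing values does not reduce it.

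**Working it through.** **Plan's own figure.** Inputs from SAP 4.2: 9.6% and 20.5%, 2:1 allocation, two-sided alpha 0.05, 95% power, continuity correction. The pooled rate is (0.096 + 2 × 0.205)/3 = 0.1687. Without the correction, the vehicle arm needs n' = [1.960√(1.5 × 0.1687 × 0.8313) + 1.645√(0.096 × 0.904 + 0.205 × 0.795/2)]² / 0.109² = 208.4. With it, n = (n'/4)[1 + √(1 + 3/(n' × 0.109))]² = 222.0. This gives 222 vehicle and 444 active, as stated.

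**Assumptions.** The documents give no Week 12 grade distribution and no dropout rate. I fixed true success at 20.5% and 9.6% and varied how successes split between grades 0 and 1, and how the rest split over grades 2, 3 and 4.

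**Formula.** With m and s the mean and SD of the grade in an arm, imputed success ≈ Φ((1.5 − m)/s).

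Example (mostly grade 3, active arm): 10% of successes are grade 0, and non-successes split 25/65/10 over grades 2/3/4.
- Shares for grades 0 to 4: 0.0205, 0.1845, 0.19875, 0.51675, 0.0795.
- m = 0.1845 + 0.3975 + 1.55025 + 0.318 = 2.450.
- s² = (0.1845 + 0.795 + 4.65075 + 1.272) − 2.45025² = 0.8985, so s = 0.948.
- Φ((1.5 − 2.450)/0.948) = Φ(−1.002) = 15.8%, against a true 20.5%.

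| Assumed distribution (grade 0 share of successes; grades 2/3/4 share of non-successes) | m, s active | m, s vehicle | Imputed success, active / vehicle (true 20.5 / 9.6) |
|---|---|---|---|
| Mostly grade 3 (10%; 25/65/10) | 2.450, 0.948 | 2.663, 0.797 | 15.8% / 7.2% |
| Mostly grade 2 (10%; 60/36/4) | 2.124, 0.815 | 2.292, 0.714 | 22.2% / 13.4% |
| More clear (30%; 40/50/10) | 2.290, 1.010 | 2.508, 0.859 | 21.7% / 12.0% |
| Severe-heavy (15%; 25/50/25) | 2.559, 1.085 | 2.794, 0.930 | 16.4% / 8.2% |

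**Whole-trial effect.** Arm shift = share missing × (imputed rate − true rate). For the first row at 12% missing: 0.12 × (15.81 − 20.50) = −0.56 active, 0.12 × (7.22 − 9.60) = −0.29 vehicle, difference 10.62.

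| Distribution | 12% missing: shift active / vehicle, difference | 20% missing: shift active / vehicle, difference |
|---|---|---|
| Mostly grade 3 | −0.56 / −0.29, 10.62 | −0.94 / −0.48, 10.44 |
| Mostly grade 2 | +0.20 / +0.45, 10.65 | +0.34 / +0.75, 10.49 |
| More clear | +0.15 / +0.29, 10.75 | +0.24 / +0.49, 10.66 |
| Severe-heavy | −0.49 / −0.17, 10.58 | −0.81 / −0.28, 10.36 |

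Three further assumed distributions gave imputed rates of 17.3% / 6.7%, 20.9% / 10.0% and 24.5% / 13.2%. Their differences among imputed subjects are 10.6, 10.9 and 11.3 points, so at 20% missing the trial difference moves by 0.2 × (−0.3, 0, +0.4) = −0.06, 0 and +0.08.

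**Simulation.** Large simulations of baseline, Week 4, 8 and 12 IGA used 12% missing, either at random or depending on Week 8 IGA. They gave the same pattern. Categorical imputation from the same earlier grades recovered the true rate among missing subjects within about 0.5 points. At trial size (467 and 233, 10-20% missing), by-arm cumulative-logit imputation kept arm rates within about 0.1 point of truth, against about 0.3 to 0.6 points for normal-plus-rounding. There the treatment difference moved by only about 0.1 point under either method.

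**Inference.** The SE of the difference is √(0.205 × 0.795/467 + 0.096 × 0.904/233) = 2.7 points. The continuity-corrected approximation at 467/233, ignoring imputation variance, gives 96.0% power without the error, 94.7-95.4% at 12% missing and 93.8-95.0% at 20%.

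**The case against.** The strongest reply is that the error is negligible and errs on the safe side. A loss of 0.3 points is 0.3/2.7 = 0.11 SE. The test is a logistic regression, and the odds ratio barely moves. At 12% missing it goes from (0.205/0.795)/(0.096/0.904) = 2.43 to 2.34 in the least favourable row (mostly grade 2), and the unadjusted Wald z from 3.55 to 3.45. If the arms are alike in outcome and missingness, by-arm imputation shifts both equally in large samples, so no false-positive risk is shown. Two planned analyses also avoid rounding. This all stands, and it limits the point to an improvement.

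The sensitivity analyses are not a full answer. The logistic imputation drops Week 4 and Week 8 IGA, and the GEE imputes nothing. A disagreement with the primary result could not be traced to rounding alone, and neither analysis replaces the primary estimate.

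A reader might infer that rounding turns the best imputed responders into failures, since a draw below −0.5 becomes −1, which is literally neither 0 nor 1. The numbers do not support giving this weight. In the four distributions, such draws are at most about 0.3% in the active arm: Φ((−0.5 − 2.290)/1.010) = 0.3%. Most out-of-range draws exceed 4.5 and are failures either way. The options placeholder in the Protocol's code could also hold bounds, though bounds would not correct the area below 1.5.

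**Conclusion.** The point holds as a modest specification flaw in the primary analysis of a co-primary. With 10-20% missing, success among imputed subjects is off by roughly −5 to +4 points. Arm-level rates shift mostly by 0.2 to 0.8 points (largest 0.94, at 20% missing). The difference changes by about 0 to 0.3 points of 10.9 at 10-12% missing and by up to about 0.5 at 20%, usually towards a smaller difference. The conclusion is unlikely to change.

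A reader might infer that every imputed value gets a wrong success probability, or that the treatment difference is always biased. Neither follows. Some distributions give almost the true rate (20.9% / 10.0%), and one gives a slightly larger difference. The sign within an arm cannot be settled, because the documents state neither the grade distribution nor the amount of missing data.

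**What to change.** In SAP 7.3.1.2 and Protocol 11.7, keep imputation by arm from baseline, Week 4 and Week 8 IGA, but impute IGA as an ordinal variable with PROC MI and FCS LOGISTIC (cumulative logit). Derive both the primary success and the secondary 2-grade success from the imputed grades. Delete the rounding sentence. In the same edit, name the procedure consistently: the SAP says PROC MCMC, the Protocol PROC MI with an MCMC statement.

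The cost is a short wording change and a few lines of code in the same procedure, made before the SAP is finalised and the blind is broken. Sparse grades, mainly in the vehicle arm (about 0.096 × 233 = 22 expected successes), need a pre-specified rule: merge adjacent grades or use an augmented likelihood. The change does not address data missing not at random.
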